A Simulation Study Comparing Successful Administration, Time to Administer, and User Experience of Ready-to-Use Nasal Glucagon with Reconstitutable Injectable Glucagon

Rationale:

The aim of this study is to compare successful administration rates, time and experience of administering nasal glucagon (NG) with those of commercially available glucagon emergency kit (GEK) during a simulated severe hypoglycemia emergency. Two different groups of participants will undergo the simulations. One group will be trained to use each device, in a similar way to the training given to real-life caregivers, close friends or family members of a person with diabetes (PWD); the other group will not be given such training, to approximate the real-life experience of colleagues or acquaintances of a PWD. During the simulations, both types of participants will have to administer treatment to a manikin that represents a person with severe hypoglycemia.

The outcomes from these simulations will be measured quantitatively (the proportion of participants administering a successful dose of NG and GEK, and how long it takes) and qualitatively (via user-questionnaires that measure ease of use, confidence and other factors).

Objective(s)/Endpoints:

Objectives	Endpoints
Primary	
To test the hypothesis that more Trained Users can successfully administer NG than GEK when treating a simulated episode of severe hypoglycemia.	The percentage of Trained Users that perform a successful administration (complete dose delivered and all critical steps completed), both for NG and GEK.
Secondary	
To test the hypothesis that more Untrained Users can successfully administer NG than GEK when treating a simulated episode of severe hypoglycemia.	The percentage of Untrained Users that perform a successful administration (complete dose delivered and all critical steps completed), both for NG and GEK.
To compare the average time to successfully administer NG, compared with GEK.	The time taken by Trained Users and Untrained Users to successfully administer NG or GEK (complete dose delivered and all critical steps completed), as measured by study site staff.
To compare percentages of users who complete critical administration steps for both NG and GEK.	The percentages of Trained Users and Untrained Users who complete all of the critical steps for both NG and GEK, as assessed by site staff.
To assess the number of simulations that result in successful administration of NG.	The percentage of all simulations that result in a successful administration of NG, for all users combined.

Objectives	Endpoints
To assess whether, overall, one device (NG or GEK) is preferred over the other.	The percentage of participants (Trained Users, PWDs and Untrained Users) that prefer one device over the other, as recorded in a questionnaire.
To assess overall ease of use of both devices (NG and GEK).	The 'ease of use' questionnaire ratings given to NG and to GEK by Trained Users, PWDs and Untrained Users.

Summary of Study Design:

Study I8R-MC-IGBM is a single-center, crossover study assessing the use of NG and GEK during a simulation of a severe hypoglycemia episode, with 2 cohorts of participants: Trained Users (Part A) and Untrained Users (Part B).

Each participant will take part in 2 simulations, 1 with NG and 1 with GEK. Quantitative results (whether or not a dose is administered successfully, and how long it takes) will be recorded by site staff during each simulation.

Qualitative results (the opinions of Trained Users, Untrained Users and PWDs) will be captured via questionnaires, both during and at the end of the study.

Study Arms and Planned Duration for an Individual Participant:

In **Part A**, each Trained User and the accompanying PWD will attend 3 one-day study visits, over the course of approximately 2 weeks:

- An initial training visit
- Two study visits, each involving a simulation of a severe hypoglycemia emergency, which the Trained User will attempt to treat with NG and GEK in turn (in randomized order).

In **Part B**, each Untrained User will attend 2 study visits over the course of approximately 1 week. Each visit will include 1 simulated severe hypoglycemia emergency, which the participant will attempt to treat with NG and GEK in turn (in randomized order).

Number of Participants:

Approximately 72 participants (39 Trained Users and 33 Untrained Users) will be recruited to ensure that 52 participants (26 Trained Users and 26 Untrained Users) complete the study.

Trained Users will be recruited such that, of the completers, half (i.e. at least 13) of the accompanying PWDs have type 1 diabetes mellitus (T1DM), and half (at least 13) have type 2 diabetes mellitus (T2DM).

Each Trained User will be accompanied at each visit by the PWD with whom they are recruited to the study.

Statistical Analysis:

The McNemar test will be used to assess the primary objective of the study (successful administration of doses in Part A of the study, with Trained Users). The exact-sign test will be used as a sensitivity analysis for the primary objective.

Successful administration will be assessed for each cohort:

- NG (Trained User) versus GEK (Trained User)
- NG (Untrained User) versus GEK (Untrained User)

For Part A (Trained Users), assessment of successful administration will also be stratified between those users who have an accompanying PWD with T1DM, and those who have an accompanying PWD with T2DM.

For baseline data, continuous variables will be presented using simple descriptive statistics such as mean, standard deviation, median and range. Categorical variables will be presented as n/N and percentage.

Time to administer a dose will be assessed, making the following comparisons:

- NG (Trained User) versus GEK (Trained User)
- NG (Untrained User) versus GEK (Untrained User)
- NG (Trained User) versus NG (Untrained User)
- GEK (Trained User) versus GEK (Untrained User)

This analysis, using descriptive statistics, will be assessed for successful and unsuccessful administration combined, as well as successful administration only.

2. Schedule of Activities

Study Schedule Protocol I8R-MC-IGBM: Part A (Trained Users)

Procedure	Study Visits			Comments
	Visit 1	Visit 2	Visit 3	
	Day 1	Days 8-9	Days 15-17	
Evaluation of Eligibility	X			Prescreening will be conducted by telephone before Visit 1. For details on evaluation of eligibility, see Section 6.
Informed Consent	X			
Randomization	X			Randomization will be stratified by diabetes type of PWD (T1DM, T2DM).
PWD Trained on Device 1 by Staff	X			This training should take no longer than 30 minutes, including questions.
“Memory Decay” Period	X			The “memory decay” period will last 55 to 60 minutes and include a short distractor task. See Section 5.1.3.5.
Participant Trained on Device 1 by PWD	X			Site staff should allow up to 30 minutes for the PWD to train the participant.
Simulation		X	X	The simulation at Visit 2 is with Device 1. The simulation at Visit 3 is with Device 2. See Table IGBM.2 for randomization schedule and Section 5.1.3.3 for details of simulations.
Participant completes NASA TLX		X	X	
PWD Trained on Second Device by Staff		X		This training should take no longer than 30 minutes, including questions.
“Memory Decay” Period		X		The “memory decay” period will last 55 to 60 minutes and include a short distractor task. See Section 5.1.3.5.
Participant Trained on Second Device by PWD		X		Site staff should allow up to 30 minutes for the PWD to train the participant.
Questionnaires			X	After the simulation at Visit 3, each PWD and Trained User will watch a video showing both simulations. Then, after a delay of 55 to 60 minutes, each PWD and Trained User will answer the comparative and individual-device questionnaires. See Section 5.1.3 for the order of questionnaires and Section 9.10 for detail of questions.
Safety Assessment/ Follow-up/Early Discontinuation	X	X	X	The safety assessment covers any accidents during training or simulations (see Section 9.4), or significant errors (e.g. insulin was administered during the simulation instead of glucagon). For follow-up of discontinued participants see Section 8.

Abbreviations: NASA = National Aeronautics and Space Administration; PWD = person with diabetes; T1DM = type 1 diabetes mellitus; T2DM = type 2 diabetes mellitus; TLX = Task Load Index.

Study Schedule Protocol I8R-MC-IGBM: Part B (Untrained Users)

Procedure	Visit 1	Visit 2	Comments
	Day 1	Days 8-9	
Evaluation of Eligibility	X		Prescreening to be conducted by telephone. For details on evaluation of eligibility, see Section 6 .
Informed Consent	X		
Randomization	X		
Simulation with Device 1	X		
NASA TLX on Device 1	X		
Simulation with Device 2		X	
NASA TLX on Device 2		X	
Questionnaires		X	After the simulation at Visit 2, each Untrained User will watch a video showing both simulations. Then, after a delay of 55 to 60 minutes, each Untrained User will answer the comparative and individual-device questionnaires (Section 9.10).
Safety Assessment/ Follow-up/Early Discontinuation	X	X	The safety assessment covers any accidents during simulations (see Section 9.4), or significant errors (e.g. insulin was administered during the simulation instead of glucagon). For follow-up of discontinued participants, see Section 8 .

Abbreviations: NASA = National Aeronautics and Space Administration; TLX = Task Load Index.

3. Introduction

3.1. Study Rationale

The aim of this study is to assess how well different groups of people – those who have received training and those who have not – are able to use nasal glucagon (NG), compared with a commercially available glucagon emergency kit (GEK) delivered via the intramuscular route, during simulations of severe hypoglycemia emergencies. Assessment of the participants' performance will take 2 forms:

- Quantitative: The proportion of participants who deliver complete doses, and follow all critical steps for dose administration, and the time it takes to deliver a dose, as recorded by study site staff;
- Qualitative: the user experience, as recorded in questionnaires. Questions include preference for either device, confidence using each device, and ease of use.

In this protocol, participants who are given instructions on each device prior to the simulations are referred to as “Trained Users”. They will be caregivers, family members or people otherwise close to a person with diabetes (PWD). Before each simulation, they will receive training from their accompanying PWD in the use of the glucagon rescue devices; this is intended to approximate the training that caregivers and relatives are likely to receive from PWDs in real life.

Study participants who are not given instructions on each device prior to the simulations are referred to as “Untrained Users”. These are intended to approximate the real-life colleagues or acquaintances of a PWD, who may be present during a severe hypoglycemia emergency and willing to step in, but are not likely to have received training on the rescue device.

The study involves simulations of severe hypoglycemia emergencies using manikins. No drug will be administered to people.

3.2. Background

Hypoglycemia, one of the most serious acute complications of diabetes treatment, is defined as an abnormally low blood glucose level that exposes the individual to potential harm. The use of glucagon is indicated for the treatment of hypoglycemia in people unable or unwilling to consume carbohydrates by mouth, according to American Diabetes Association (ADA) guidance (ADA 2018). ADA guidance identifies a 3-stage classification of hypoglycemia:

Level	Glycemic criteria	Description
Hypoglycemia alert value (level 1)	≤ 70 mg/dL (3.9 mmol/L)	Sufficiently low for treatment with fast-acting carbohydrate and dose adjustment of glucose-lowering therapy
Clinically significant hypoglycemia (level 2)	≤ 54 mg/dL (3.0 mmol/L)	Sufficiently low to indicate serious, clinically important hypoglycemia
Severe hypoglycemia (level 3)	No specific glucose threshold	Hypoglycemia associated with severe cognitive impairment requiring external assistance for recovery

Source: ADA Standards of Medical Care in Diabetes – 2018.

Based on this classification, the ADA recommends that glucagon should be prescribed for all individuals at increased risk of clinically significant hypoglycemia (level 2), so that glucagon is available should it be needed. Furthermore, an individual does not need to be a healthcare professional to safely administer glucagon.

Nasal glucagon, also known as LY900018, is an investigational drug-device combination product intended for the treatment of severe hypoglycemia (level 3 in the ADA guidance), in adult and pediatric PWDs. Nasal glucagon consists of a single-use nasal dosing device that delivers a fixed 3-mg dose of glucagon powder, absorbed passively through the nasal mucosa.

Nasal glucagon is being developed as an alternative to commercially available GEKs for treatment of severe hypoglycemia, with a needle-free device and fewer steps for administration.

3.3. Benefit/Risk Assessment

This study does not involve the dosing of study drug to humans. As such, there is no expected benefit to study participants. During each simulation with a GEK, there is a risk that participants may suffer a needle-stick injury, which may also result in accidental administration of the marketed comparator product. Site staff will closely monitor simulations and respond to any such safety issues that arise.

4. Objectives and Endpoints

Table IGBM.1 shows the objectives and endpoints of the study.

Table IGBM.1. Objectives and Endpoints

Objectives	Endpoints
Primary	
To test the hypothesis that more Trained Users can successfully administer NG than GEK when treating a simulated episode of severe hypoglycemia.	The percentage of Trained Users that perform a successful administration (complete dose delivered and all critical steps completed), both for NG and GEK. See Section 5.1.3.4 for definitions of complete dose and critical steps.
Secondary	
To test the hypothesis that more Untrained Users can successfully administer NG than GEK when treating a simulated episode of severe hypoglycemia.	The percentage of Untrained Users that perform a successful administration (complete dose delivered and all critical steps completed), both for NG and GEK. See Section 5.1.3.4 for definitions of complete dose and critical steps.
To compare the average time to successfully administer NG, compared with GEK.	The time taken by Trained Users and Untrained Users to successfully administer NG or GEK (complete dose delivered and all critical steps completed), as measured by site staff.
To compare percentages of users who complete critical administration steps for both NG and GEK.	The percentages of Trained Users and Untrained Users who complete all of the critical steps for both NG and GEK, as assessed by site staff.
To assess the number of simulations that result in successful administration of NG.	The percentage of all simulations that result in a successful administration of NG, for all users combined.
To assess whether, overall, one device (NG or GEK) is preferred over the other.	The percentage of participants (Trained Users, PWDs and Untrained Users) that prefer one device over the other, as recorded in a questionnaire.
To assess overall ease of use of both devices (NG and GEK).	The 'ease of use' questionnaire ratings given to NG and to GEK by Trained Users, PWDs and Untrained Users.

Objectives	Endpoints
Exploratory To assess participants' overall confidence in the use of NG and GEK devices.	The 'confidence' questionnaire ratings given to NG and to GEK by Trained Users, Untrained Users and PWDs.
To compare the time it takes a PWD to teach the use of NG and GEK devices.	The average length of time taken by PWDs to teach the use of NG and GEK to their associated Trained User, as measured by site staff.
To compare participants' experience of Mental Demand, Effort, Frustration and other elements of the NASA Task Load Index, following NG and GEK simulations.	Ratings given by Trained Users and Untrained Users in the NASA Task Load Index to describe their experiences with NG and GEK.

Abbreviations: GEK = glucagon emergency kit; NASA = National Aeronautics and Space Administration; NG = nasal glucagon; PWD = person with diabetes.

5. Study Design

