5.4. Scientific Rationale for Study Design

The use of a crossover design allows a within-participant comparison of NG with GEK.

The use of 2 groups of participants, Trained User and Untrained User, is intended to simulate the types of people in the real world who are typically required to administer glucagon in an emergency: caregivers/relatives/close friends of PWDs who have received instruction in how to administer glucagon; and colleagues or acquaintances who have not received instruction, but still may be willing to step in.

The process of a PWD relaying instructions to the Trained User – rather than the Trained User receiving instruction first-hand from site staff – is intended to simulate the real-life tendency for PWDs to learn from a medical professional how to use a GEK, and to later relay this information to caregivers, relatives and/or close friends. The “memory decay” period is intended to simulate the delay that occurs in relaying these instructions.

A manikin will represent a person experiencing severe hypoglycemia; this allows for better control of the variables of each simulation, and avoids ethical issues related to the induction of severe hypoglycemia in people.

The PWD will not observe simulations in real time, so as to minimize the risk of their intervening or otherwise influencing the Trained User. This is intended to ensure simulations are like-for-like between participants and between devices, which will aid comparison.

In Part A, the manikin will appear to have the same gender as the PWD, and will be referred to with the PWD’s name, to simulate the increased stress and pressure of treating a relative or close

friend. In Part B, this is not a pertinent factor, and manikins will default to being male in appearance.

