Additionally, **weights** will be calculated for each the scales. This will be carried out using comparison cards, on which each scale is compared to the 5 other scales, creating a total of 15 comparison cards. The subject needs to choose, for each comparison, which scale was the most demanding for the task. For each time a scale was selected by the subject, a value of 1 is added to its weight. As each scale is compared to the other 5 scales exactly ones, the maximum of the weight is 5 (this scale was always selected as being the most demanding) and the minimum is zero (this scale was never selected as being the most demanding).

For the analyses, a weighted average of the 100-point-scale scores will be computed in the analysis datasets for each subject and administration method (NG / GEK).

Questionnaire Comparing Both Devices

For Trained Users and Untrained Users, the comparative questionnaire will include questions on preference, ease of use and confidence using each device.

Person with diabetes will receive a differently worded questionnaire that will include questions on their preference of device, and their impression of the user experience for ease of use and confidence.

Device-Specific Questionnaires (NG and GEK)

All participants (Trained Users, Untrained Users and PWDs) will answer 2 device-specific questionnaires, regarding NG and GEK individually. These will include questions related to ease of use and confidence in using each device, without comparing to the other device.

All questionnaire data will be listed and summarized by part and treatment. For Part A (Trained Users), summaries will also be stratified between those users who have an accompanying PWD with T1DM, those who have an accompanying PWD with T2DM and overall.

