9.5 Statistical Methodology

The following endpoints will be summarized by treatment using descriptive statistics and listed:

- The percentage of Trained Users and Untrained Users that perform a successful administration
- The time taken by Trained Users and Untrained Users to successfully administer NG or GEK
- The percentages of Trained Users and Untrained Users who complete all of the critical steps
- The percentage of all simulations that result in a successful administration of NG, for all users combined
- The average length of time taken by PWDs to teach the use of NG and GEK to their associated Trained User,

The McNemar test will be used to assess the percentage of Trained Users that perform a successful administration. The exact-sign test will be used as a sensitivity analysis.

Successful administration will be assessed, for each cohort:

- NG (Trained User) versus GEK (Trained User)
- NG (Untrained User) versus GEK (Untrained User)

Example SAS code for the McNemar test

```
proc freq data = success;
  weight count / zeros;
  tables NG_trained*GEK_trained / agree;
  exact mcnem;
run;
```

Example SAS code for the exact-sign test

```
proc univariate data=success;
  var success_diff;
run;
```

Where `success_diff` is 1 if NG is successful and GEK is not, 0 if both treatments are successful or not successful and -1 if NG is not successful and GEK is successful.

For Part A (Trained Users), assessment of successful administration will also be stratified between those users who have an accompanying PWD with T1DM, and those who have an accompanying PWD with T2DM.

Time to administer a dose will be assessed using summary statistics, making the following comparisons:

- NG (Trained User) versus NG (Untrained User) – two sample t-test
- GEK (Trained User) versus GEK (Untrained User) – two sample t-test

- NG (Trained User) versus GEK (Trained User) – Paired t-test
- NG (Untrained User) versus GEK (Untrained User) – Paired t-test

This analysis, using descriptive statistics and the appropriate t-test, will be assessed for successful and unsuccessful administration combined, as well as successful administration only. Time needed to complete glucagon administration will be shown categorically based on the following categories:

- <30 seconds
- 30 seconds-45 seconds
- 45 seconds-1 minute
- 1 minute-1 minute 15 seconds
- 1 minute 15 seconds-1 minute 30 seconds
- 1 minute 30 seconds-1 minute 45 seconds
- 1 minute 45 seconds-2 minutes

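### Teaching time and NASA TLX have objectives to compare the devices, but the SAP plans only by-treatment summaries of these paired data, with no within-participant difference or interval

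*Protocol*

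**What the plan says.** Table IGBM.1 in Protocol Section 4 lists two exploratory objectives worded as comparisons: "To compare the time it takes a PWD to teach the use of NG and GEK devices" and "To compare participants' experience of Mental Demand, Effort, Frustration and other elements of the NASA Task Load Index, following NG and GEK simulations". Confidence is also exploratory, but its objective says *assess*. Two secondary objectives use that verb as well. One concerns ease of use. The other reads "To assess whether, overall, one device (NG or GEK) is preferred over the other", and its endpoint is "The percentage of participants (Trained Users, PWDs and Untrained Users) that prefer one device over the other, as recorded in a questionnaire".

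Protocol 5.4 gives the reason for the design: "The use of a crossover design allows a within-participant comparison of NG with GEK".

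For analysis, SAP 9.5 places teaching time last in a list introduced by "The following endpoints will be summarized by treatment using descriptive statistics and listed", and nothing further is specified for it. SAP 9.4 defines one weighted TLX score per subject and device, then closes the questionnaire section with "All questionnaire data will be listed and summarized by part and treatment", adding a breakdown by diabetes type in Part A. SAP 9.1 presents statistics and analyses only where the SAP details them.

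The SAP does use the pairing elsewhere: McNemar and exact-sign tests for success, and paired t-tests for administration time.

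**The concern.** An objective to compare two devices in a crossover calls for an estimate of the within-person difference and its uncertainty. Two columns of means and SDs supply neither the standard error nor the interval of that difference, because both depend on the within-person correlation, which is not reported. A reader who wants an interval from the tables has to treat the columns as independent groups, which is the wrong error structure for these data.

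This is not a general rule of keeping non-primary endpoints descriptive. Protocol 10.3 describes the administration-time analysis as descriptive, and the SAP adds t-tests to it. Teaching time and TLX receive no such treatment.

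The device-specific ratings have a further complication. Protocol 5.1.3.1, 5.1.3.2 and 9.10 withhold a device's questionnaire if the user did not attempt that device, so the NG and GEK columns may describe different people. Subtracting their means would then not give the within-person difference. SAP 9.4 says that everyone answers both questionnaires and does not address this.

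For preference, the question is *whether* one device is preferred. A bare percentage from a small group does not show whether the result is compatible with no preference.

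**Working it through.** **The plan's own figure.** The only design figure is 90% power for the primary endpoint (Protocol 10.1: 26 pairs, 90% vs 50% success, 45% discordant, two-sided 0.05). With d = 0.40 and ψ = 0.45, power = Φ[(d√n − 1.96√ψ)/√(ψ − d²)] = Φ[(2.040 − 1.315)/0.539] = 91.1%. Exact enumeration of the two-sided sign test gives 90.8%. The figure reproduces, but it says nothing about the endpoints here, for which the plan gives no precision figure.

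**Where each endpoint stands**

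| Endpoint | Level, verb | Data | Planned output |
|---|---|---|---|
| Teaching time | exploratory, compare | paired within Part A dyad | summary by treatment |
| NASA TLX | exploratory, compare | paired within user | summary by part and treatment |
| Confidence, device-specific | exploratory, assess | paired if both devices attempted | summary by part and treatment |
| Ease of use, device-specific | secondary, assess | paired if both devices attempted | summary by part and treatment |
| Preference | secondary, assess whether | one choice per person | summary by part and treatment |

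The last row does not fit its planned output. A choice between two devices cannot be summarised by treatment, and no denominator is given.

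**Precision of the NG minus GEK mean difference**, in units of a common SD. Input: n = 26 (Protocol 10.1). The within-person correlation ρ for these endpoints is not in the documents, so it is assumed over a range. Protocol 10.1 mentions a moderate within-subject correlation, but only for success.

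- Read as independent groups: t(0.975, 50) × √(2/26) = 2.009 × 0.277 = 0.557.
- Paired: t(0.975, 25) × √(2(1 − ρ)/26) = 2.060 × 0.277 × √(1 − ρ).

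| Assumed ρ | Paired half-width (SD) | Ratio to 0.557 |
|---|---|---|
| 0 | 0.571 | 1.03 |
| 0.3 | 0.478 | 0.86 |
| 0.5 | 0.404 | 0.73 |
| 0.7 | 0.313 | 0.56 |

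As an illustration on the 0–100 TLX scale with an assumed SD of 20 points, the paired half-widths are 11.4, 9.6, 8.1 and 6.3 points, against 11.1 for the independent reading.

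**Preference in one group of 26** (Clopper-Pearson interval, exact two-sided binomial test against 50%).

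- 18/26 (69%): 48% to 86%, p = 0.076.
- 19/26 (73%): 52% to 88%, p = 0.029.

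So any majority from 14 to 18 of 26 is compatible with no preference.

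**Preference over all three groups.** There are up to 3 × 26 = 78 respondents. If they are treated as independent, which is only approximate because a Trained User and the accompanying PWD form a dyad, 48/78 (62%) gives 50% to 72% (lower limit 49.8%, p = 0.054) and 49/78 (63%) gives 51% to 74% (p = 0.031). The 19/26 threshold therefore applies to group results, not to the overall one.

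**The case against.** The best defence is that teaching time, TLX and confidence are exploratory, that *assess* objectives can properly be met descriptively, and that the ease-of-use endpoint is simply the ratings given to each device, which a by-treatment summary delivers. Individual data are listed, so paired differences could be rebuilt from the listings. Among people with both values, the point difference is the subtraction of two means. Protocol 10.3 and SAP Section 3 allow additional analyses, and the TFL shells, which are not among the documents, may hold more detail.

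Much of this stands and limits the point. It does not remove it. For teaching time and TLX, the plan states a comparison and specifies none. Permission for extra analyses does not say which ones, and choosing them after open-label data have been seen is what prespecification is meant to avoid.

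A reader might also infer more than the documents support:

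- *That preference loses the pairing.* It does not. It comes from the comparative questionnaire, in which each person compares the two devices directly.
- *That ease of use and confidence rest only on separate device summaries.* The comparative questionnaire covers both (Protocol 9.10.2, SAP 9.4). The gap concerns the device-specific ratings.
- *That SAP 9.6 forbids a comparison.* It covers assessments not detailed elsewhere, and these are detailed. SAP 9.1 is the relevant limit.
- *That pairing must sharpen the result.* At zero correlation the paired interval is slightly wider.

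**Conclusion.** The point holds for teaching time and NASA TLX, where a comparison is the stated objective, the data are paired, and neither a difference nor an interval is planned. It holds with less force for the device-specific ease-of-use and confidence ratings. For preference, only an interval and a properly defined summary are missing.

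The gain from pairing rests on an assumed positive within-person correlation, equal SDs and 26 complete pairs. Over correlations of 0.3 to 0.7 the interval is about 14% to 44% narrower than the independent reading. Even without that gain, the paired interval is the one that matches the design. The endpoints are mostly exploratory and the primary conclusion is untouched, so this is a worthwhile low-cost improvement and not a flaw in the trial's main inference.

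**What to change.** In SAP 9.4 and 9.5, report the within-participant NG minus GEK difference with a 95% CI among people with both values, and state the paired n. Use a paired t interval, or a Hodges-Lehmann interval for ordinal ratings:

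- Teaching time: Part A dyads only, since Untrained Users receive no teaching.
- NASA TLX composite and six scales: Trained Users and Untrained Users, since PWDs do not complete it.
- Device-specific ease of use and confidence: Trained Users, PWDs and Untrained Users separately. Note that a questionnaire is withheld when the device was not attempted, and align SAP 9.4 with Protocol 9.10 on this.
- Preference: the proportion preferring NG with an exact 95% CI in each group, with its denominator, in place of a summary by treatment.

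Label all intervals descriptive and unadjusted.

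The cost is SAP text and table programming, with no new data, visits or participants. The downside is about two dozen unadjusted intervals: 7 × 2 = 14 for TLX, 1 for teaching time, 3 each for ease of use and confidence, and 3 for preference, 24 in all if each rating is a single item.
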